## **8.2.16.** Visit 21 (Month 18/Week 78) – Hospital Visit

Rituximab maintenance dosing and imaging, as outlined in Table 8-19.

Table 8-19 Procedures and assessments at Visit 21 (Month 18/Week 78 [±7 days])

Assessment or Procedure	Explanation	
Concomitant medication	Recording of concomitant medication used since the previous visit	
Physical examination	Any abnormal findings will be recorded in the AE record	
Vital signs	Systolic/diastolic blood pressure, heart rate and body temperature	
ECOG	ECOG performance status	
Haematology	Including haemoglobin, platelet count, white blood cell count and differential (absolute count of neutrophils, lymphocytes, monocytes, eosinophils and basophils)	
Serum biochemistry	Including sodium, potassium, calcium, magnesium, creatinine, urea, uric acid, ALP, ASAT, ALAT, LDH, GGT, glucose, total bilirubin and albumin	
Immunogenicity	Monitoring ADA response (lilotomab, Betalutin, RTX)	
Bone marrow biopsy	BM biopsy required for initial confirmation of CR if patient had BM infiltration at baseline	
Radiology - CT scans with contrast or MRI	CT or MRI of neck, thorax, abdomen and pelvis. Information about contrast medium, target lesion location and measurements and non-measurable lesions will be recorded. The same camera should preferably be used throughout the study	
Rituximab administration 375 mg/m  i.v. or 1400 mg s.c.	Weight, body surface area, dose administered, start and end time of administration and pre-medication will be recorded	

Assessment or Procedure	Explanation	
Adverse events	Any AEs occurring since prior visit will be recorded	

## **8.2.17.** Visit 22 (Month 21/Week 91) – Hospital Visit

Rituximab maintenance dosing, as outlined in Table 8-20.

Table 8-20 Procedures and assessments at Visit 22 (Month 21/Week 91 [±7 days])

Assessment or Procedure	Explanation
Concomitant medication/therapy	Recording of concomitant medication used since the previous visit
Physical examination	Any abnormal findings will be recorded in the AE record
Vital signs	Systolic/diastolic blood pressure, heart rate and body temperature
ECOG	ECOG performance status
Haematology	Including haemoglobin, platelet count, white blood cell count and differential (absolute count of neutrophils, lymphocytes, monocytes, eosinophils and basophils)
Serum biochemistry	Including sodium, potassium, calcium, magnesium, creatinine, urea, uric acid, ALP, ASAT, ALAT, LDH, GGT, glucose, total bilirubin and albumin
Rituximab administration 375 mg/m  i.v. or 1400 mg s.c.	Weight, body surface area, dose administered, start and end time of administration and pre-medication will be recorded
Adverse events	Any AEs occurring since prior visit will be recorded

## **8.2.18.** Visit 23 (Month 24/Week 104) – Hospital Visit

Rituximab maintenance dosing and imaging, as outlined in Table 8-21.

Table 8-21 Procedures and assessments at Visit 23 (Month 24/Week 104 [±7 days])

Assessment or Procedure	Explanation	
Concomitant medication	Recording of concomitant medication used since the previous visit	
Physical examination	Any abnormal findings will be recorded in the AE record	
Vital signs	Systolic/diastolic blood pressure, heart rate and body temperature	
ECOG	ECOG performance status	
Haematology	Including haemoglobin, platelet count, white blood cell count and	
	differential (absolute count of neutrophils, lymphocytes,	
	monocytes, eosinophils and basophils)	
Serum biochemistry	Including sodium, potassium, calcium, magnesium, creatinine,	
	urea, uric acid, ALP, ASAT, ALAT, LDH, GGT, glucose, total	
	bilirubin and albumin	
Immunogenicity	Monitoring ADA response (lilotomab, Betalutin, RTX)	
Minimal Residual Disease 	MRD monitoring to assess early treatment response and detect	
(peripheral blood sample)	relapse	
Bone marrow biopsy	BM biopsy required for initial confirmation of CR if patient had	
	BM infiltration at baseline	
Radiology - CT scans with	CT or MRI of neck, thorax, abdomen and pelvis. Information	
contrast or MRI	about contrast medium, target lesion location and measurements	
	and non-measurable lesions will be recorded. The same camera	
	should preferably be used throughout the study	
Rituximab administration	Weight, body surface area, dose administered, start and end time	
$375 \text{ mg/m}^2 \text{ i.v. or } 1400 \text{ mg s.c.}$	of administration and pre-medication will be recorded	

Assessment or Procedure	Explanation
Adverse events	Any AEs occurring since prior visit will be recorded

Mandatory, unless relapse or disease progression has been clinically observed

#### **8.2.19.** End of study visit – Hospital Visit

The end of study visit should occur:

- 28 days (± 3 days) post last rituximab administration for patients, who complete the study per protocol (Month 25/Week 108)
- Within 7 days of decision of withdrawing from the study is made if the decision occurs > 28 days post last administration of study treatment for patients who discontinue from the study before Month 24 (e.g. disease progression, start of new anti-cancer therapy, other reason) An end of study visit is not expected for patients, who discontinue due to death, lost to follow up or withdrawal of consent.

Safety follow-up procedures 4 weeks after administration of the final RTX study dose are outlined in Table 8-22.

Patients in survival follow-up at the time of Protocol v4.0 approval can have the EOS visit at their next scheduled visit or an earlier convenient time point

Table 8-22 Procedures and assessments at end of study visit

Assessment or Procedure	Explanation	
Concomitant medication	Recording of concomitant medication used since the previous visit	
Physical examination	Any abnormal findings will be recorded in the AE record	
Vital signs	Systolic/diastolic blood pressure, heart rate and body temperature	
ECOG	ECOG performance status	
Haematology	Including haemoglobin, platelet count, white blood cell count and differential (absolute count of neutrophils, lymphocytes, monocytes, eosinophils and basophils)	
Serum biochemistry	Including sodium, potassium, calcium, magnesium, creatinine, urea, uric acid, ALP, ASAT, ALAT, LDH, GGT, glucose, total bilirubin and albumin	
Adverse events	Any AEs / AESIs occurring since prior visit will be recorded	

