	Two cohorts of 3-6 patients will be initially evaluated for dose limiting toxicity before determining the subsequent Betalutin dose for the remainder of the study. Dose-escalation decisions will be made by the Investigator(s) and Sponsor following review of the safety data once haematologic recovery has occurred.
	After the last dose of rituximab, vital signs, ECG (final visit only), physical examination, haematology, serum biochemistry, Adverse Drug Reaction (ADR) and Adverse Events of Special Interest (AESI) will be collected at an end of study visit that will occur at least 28 days post last administration of study treatment. Patients in survival follow-up at time of Protocol v4.0 approval can have the EOS visit at their next scheduled visit or an earlier convenient time point.
Pharmacokinetics and biodistribution	Total radioactivity measurements in blood will be performed at certain intervals until Day 28. Mandatory at Radium Hospital (Oslo, Norway) only, otherwise optional. Patients will undergo SPECT imaging at certain time points in order to measure distribution of

	Betalutin in the body and calculate absorbed radiation dose to target organs/tissues and tumours.
Biomarker assessments	Biomarkers assessments including CD20 and CD37 expression in tumour tissue biopsy and immunophenotyping of circulating lymphocyte subsets (absolute cell counts), will be performed at various time points throughout the study
Other biomarker studies on additional samples	Biomarkers including but not exclusive to MRD (blood) and gene expression changes related to disease treatment in tumour tissue (archival or newly collected biopsy at screening, relapse or disease progression), will be assessed at various time points throughout the study. Patient's major histocompatibility complex (MHC) class I/II haplotype will be defined using peripheral blood (DNA) or saliva (DNA). Anti-tumour T-cell responses will be explored by flow cytometry after co-culture of peripheral mononuclear cells (blood) and autologous lymphoma cells (biopsy and/or needle aspirate), and other biomarkers at selected time points throughout the study at Radium Hospital (Oslo, Norway) only.
Statistical methods and data analysis	The safety analysis population will include all patients who received at least one dose of any study drug.

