**Haematological:** Anemia, neutropenia or thrombocytopenia CTCAE (v4.03) grade 4 lasting >7 days, or grade 3 thrombocytopenia with clinically significant bleeding, or febrile neutropenia (ANC <1000/mm^3 with a temperature >38.3°C).

**Non-haematological**: An AE of CTCAE (v4.03) grade 3 or higher where the relationship to study treatment cannot be ruled out, and is not primarily related to disease, disease progression, intercurrent illness or concomitant medications that occurs within the first 12 weeks of treatment. Other clinically significant toxicities may also be considered to be DLTs by the Investigators and Sponsors, even if not CTCAE grade 3 or higher.

Responding patients (i.e. those having a CR, PR or SD response following Betalutin and the 4-weekly doses of i.v. RTX) will receive maintenance RTX every 3 months for up to 2 years (a total of 8 doses), or until disease progression, commencing at Week 14. This may be administered by either i.v. (375 mg/m²) or s.c. (fixed dose of 1400 mg) routes.

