## 7.2. Patient Withdrawal/Discontinuation from the Study

In accordance with the Declaration of Helsinki, each patient is free to withdraw from the study at any time. Investigator(s) also have the right to withdraw patients from the study in the event of illness, AEs, or other reasons concerning the health or well-being of the patient, or in the case of lack of cooperation.

Should a patient decide to withdraw after administration of the study drug(s) or should the Investigator(s) decide to withdraw the patient, all efforts will be made to complete and report the observations up to the time of withdrawal as thoroughly as possible. A complete final evaluation at the time of the patient's withdrawal (end of study visit) should be made within 28 days (± 3 days) of receiving the last study treatment administration if ending treatment per protocol, or within 7 days of taking the decision to withdraw if it occurs > 28 days after the last study treatment administration and an explanation given of why the patient is withdrawing or being withdrawn from the study. The reason and date for withdrawal must be noted in the eCRF. If the reason for withdrawal is a clinical AE or an abnormal laboratory test result, monitoring will continue until the outcome is evident. The specific event or test result(s) must be recorded in the eCRF. If the reason for withdrawal is due to disease progression, the study site should make all effort to continue with the safety monitoring.

Haematological toxicity was observed in the phase 1/2 LYMRIT-37-01 study, with nadir values 5 to 7 weeks after injection of Betalutin. It is advisable to monitor the haematology parameters of the withdrawn patients between 6 and 9 weeks after the last RTX administration or until recovery to CTCAE grade 1 or less.

Single patient study discontinuation is per definition, when the patient:

- has completed Month 24 administration of rituximab, per protocol or
- experiences one of the following situations before per protocol end of study:
  - withdraws consent to participate in the study
  - has died
  - is lost to follow up
  - has disease progression
  - starts further anticancer therapy or
- when the patient is withdrawn for a reason other than described above

CONFIDENTIAL

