#### Furthermore:

- Survival information, Adverse Drug Reaction (ADR) and Adverse Events of Special Interest (AESI) will continue to be collected for any single patient until end of study visit, consent withdrawal, lost to follow up or death
- If the patient withdraws consent for disclosure of future information, the Sponsor may retain and continue to use any data collected before such a withdrawal of consent
- If a patient withdraws from the study, he/she may request destruction of any samples taken and not tested, and the Investigator must document this in the study site records
- The Investigator and Sponsor may continue to use publicly available information to establish the survival status of patients who have withdrawn consent

See Schedule of activities (Section 1.2) for data to be collected at the time of treatment discontinuation and follow-up and for any further evaluations that need to be completed.

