#### 9.2.1. Definition

#### 9.2.1.1. Definition of adverse event

An AE is defined as the appearance of (or worsening of any pre-existing) undesirable sign(s), symptom(s) or medical condition(s) that occur after the patient signed ICF has been obtained.

An AE can be any unfavourable and unintended sign (including an abnormal laboratory finding), symptom, or disease temporally associated with the use of a study drug, whether or not considered related to the study drug.

Abnormal laboratory values or test results occurring after informed consent constitute AEs only if they induce clinical signs or symptoms, are considered clinically significant, require therapy (e.g. blood or platelet transfusion) or require changes in medications. Laboratory abnormalities that meet the criteria for AE should be followed until they have returned to normal. Laboratory abnormalities not requiring clinical intervention or further investigation will be captured as part of overall laboratory monitoring and should not be reported as AEs.

AEs that begin or worsen after informed consent should be recorded in the eCRF. Conditions that were already present at the time of informed consent should be recorded in the patient's Medical History CRF page. All AEs should be reported until 4 weeks following their last RTX maintenance dose or 12 weeks after Betalutin administration for patients who do not qualify for RTX maintenance therapy (see Section 4.1). Only ADR (see Section 9.2.1.2) and AESI (see Section 9.2.1.7) will be reported during follow-up.

Please see Section 9.2.4 for guidance on AE reporting.

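### A fully dosed patient who leaves at about Weeks 8-11 can count as DLT-free with no contact scheduled for the rest of the 12-week AE and DLT window

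*Combined protocol and SAP*

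**What the plan says.** **Exit visit.** Section 8.2.19 sets the visit for early leavers "Within 7 days of decision of withdrawing from the study is made if the decision occurs > 28 days post last administration" of study treatment. Section 7.2 carries the same condition: "or within 7 days of taking the decision to withdraw if it occurs > 28 days after the last study treatment administration". Neither section gives a time for an early leaver who decides within 28 days of the last dose. The synopsis (safety assessments) speaks only of "an end of study visit that will occur at least 28 days post last administration of study treatment".

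**End of collection.** Under Section 7.2, survival information, ADRs and AESIs "will continue to be collected for any single patient until end of study visit, consent withdrawal, lost to follow up or death".

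**AE window.** Section 9.2.1.1 requires all AEs until "12 weeks after Betalutin administration for patients who do not qualify for RTX maintenance therapy", and Section 9.2.4 repeats the 12 weeks.

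**DLT window.** Section 6.1 counts a related non-haematological event of grade 3 or higher "that occurs within the first 12 weeks of treatment". It does not say when the 12 weeks start.

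**Evaluability.** Section 6.1 asks for all doses and haematological recovery to grade 2 or better. Section 9.2.2 times the safety teleconference by haematological recovery. Neither requires 12 weeks of observation.

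**Withdrawal of consent.** Section 7.2 asks for a complete final evaluation when a patient decides to withdraw. Section 8.2.19 states: "An end of study visit is not expected for patients, who discontinue due to death, lost to follow up or withdrawal of consent".

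**The concern.** The primary endpoint (frequency and severity of AEs) and the 3+3 count both rely on the first 12 weeks. For a patient who stays, the Week 12 visit closes that window: Table 8-13 collects AEs since the prior visit, while Table 8-12 lists only blood tests for Weeks 9-11. A patient who leaves after Week 8 loses that closing visit, and the exit visit may come well before it.

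Such a patient can still be evaluable, so an unobserved stretch is read as free of DLT. Observation is lost for reasons that may be linked to outcome (progression, new anticancer therapy, the patient's own decision), and missed events can only lower the toxicity count. In cohorts of 3-6, one missed DLT turns 1/3 into 0/3 or 2/6 into 1/6, and a different rule in Section 6.1 then applies.

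**Working it through.** **1. The plan's own figures.** Two cohorts of 3-6 give 2 x 3 = 6 and 2 x 6 = 12, the stated sample size. Last induction RTX on Day 28 plus 28 days is Day 56 = Week 8, as in Section 8.2.8. Week 104 plus 28 days is Week 108, as in Section 8.2.19. All reproduce.

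**2. When the 7-day rule starts.** For a last dose on Day L it covers decisions from Day L + 29. With L = 28 that is Day 57 (Day 55 to Day 59 if the Day 28 dose uses its 2-day window).

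**3. Gap for a Day 57 decision.** The visit falls on Days 57-64.

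| 12 weeks counted from | Window ends | Days without scheduled contact |
|---|---|---|
| Betalutin, Day 0 | Day 84 | 84 - 64 = 20 to 84 - 57 = 27 (24-32% of 84) |
| First RTX, Day -14 | -14 + 84 = Day 70 | 70 - 64 = 6 to 70 - 57 = 13 |

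The second row concerns the DLT window only. The AE window is expressly counted from Betalutin, so its gap is 20-27 days either way.

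**4. Which decisions are affected.** The visit must fall before Day 84 if decision day + 7 is at most 83, that is Days 57-76. Against Day 70 the range is Days 57-62.

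**5. Decisions up to Day 56.** The 7-day rule does not apply. Under the synopsis, a visit on Day 28 + 28 = Day 56 would comply, 84 - 56 = 28 days before Week 12.

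**6. Effect on the 3+3.** A dose level passes on 0/3, or on 1/3 followed by 0/3. With true DLT rate p, the pass probability is (1 - p)^3 + 3p(1 - p)^5.

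- p = 0.20: 0.512 + 0.197 = 0.709
- p = 0.33: 0.301 + 0.134 = 0.434

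Now let one of the first three be observed for only a fraction f of that patient's DLT risk, so the detectable rate is fp, with everyone else fully observed. The pass probability becomes (1 - fp)(1 - p)^2 + [fp(1 - p)^2 + 2p(1 - p)(1 - fp)](1 - p)^3. A uniform hazard over 84 days and an exit visit on Day 64 give f = 64/84 = 0.76.

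| p | Full observation | f = 0.76 | f from 0.90 to 0.33 |
|---|---|---|---|
| 0.20 | 0.709 | 0.731 (+2.2 points) | 0.718 to 0.772 |
| 0.33 | 0.434 | 0.470 (+3.6 points) | 0.449 to 0.533 |

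The DLT rates, the hazard shape and the range of f are assumptions. The documents give no DLT rate for this combination and no dropout rate.

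**The case against.** The case on the other side is substantial.

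- **Reporting duties do not end at the exit visit.** Sections 9.2.4 and 9.2.5.1 keep all AEs and SAEs reportable to 12 weeks after Betalutin, and related SAEs at any time, with a route for those seen after the end of study visit. The clause in Section 7.2 that ends collection names survival, ADRs and AESIs, not all AEs. This stands. A reader might infer that safety reporting stops at exit; the documents do not say so. What they lack is a contact at which events would be found.
- **Section 7.2 provides monitoring after withdrawal.** It runs to outcome after an AE or laboratory withdrawal, sites are to try to continue after progression, and blood counts are advised 6-9 weeks after the last RTX (Days 70-91 for a Day 28 dose). This also stands, but none of it schedules a search for new non-haematological events.
- **Patients who missed doses cannot distort the 3+3.** A reader might take the worst case, a patient with no RTX after Day 0 whose exit visit falls on Days 29-36, as a DLT-free count that misses the nadir at Weeks 5-7. Section 6.1 makes that patient non-evaluable and Section 7.3 allows a new enrolment to be considered. Only AE completeness suffers. For an evaluable patient leaving on Day 57, Weeks 5-7 have passed with weekly counts.
- **The case may be rare.** The first scan after baseline is at Week 12, so scan-detected progression will usually coincide with an AE visit. No exit rate is given, so a probability of at least one early leaver would rest on assumption, and would also count patients who are not evaluable.
- **The cause lies partly in Sections 6.1 and 9.2.2.** Because decisions follow haematological recovery, a patient still on study could also be counted before Week 12. This stands and shapes the fix.
- **A visit cannot be required after consent is withdrawn.** True, but offering one is compatible with Section 7.2, and the two sections should agree.

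**Conclusion.** The point holds in a limited form. A patient with all doses through Day 28 and recovered counts who decides to leave on about Days 57-76 is due an exit visit before Day 84 and can count as DLT-free on a window not fully observed. For a Day 57 decision the stretch without scheduled contact is 20-27 days, or 6-13 days of DLT window if that window starts on Day -14. For decisions within 28 days of the last dose, Sections 7.2 and 8.2.19 leave the visit untimed.

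A reader might infer that everyone who leaves before Week 12 has a single exit visit within 7 days. The documents do not support this, because the rule carries the 28-day condition.

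The effect on dose selection is modest: about 2-4 points on the pass probability for one such patient, under a uniform hazard and assumed DLT rates of 0.20 and 0.33. For patients who missed doses, only completeness of the primary AE endpoint is affected. The bias is towards lower toxicity, and the passages conflict on their face, so this should be corrected.

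**What to change.** 1. Reconcile Section 8.2.19 and Section 7.2, including its clause on when collection ends, with Sections 9.2.1.1 and 9.2.4 and the DLT window in Section 6.1. State the exit-visit timing for decisions within 28 days of the last dose, consistently with the synopsis.
2. Add to Section 8.2.19: *For a patient who leaves before 12 weeks after Betalutin, AEs and the DLT criteria are also collected at 12 weeks after Betalutin, by visit or telephone, unless the patient refuses, has died or cannot be reached.*
3. Flag patients without this contact as incompletely observed in the DLT listing. This remains useful even if all enrolled patients are already past Week 12.
4. Reconcile the evaluability rule in Section 6.1 and the decision timing in Section 9.2.2 with the 12-week DLT window, and define when that window starts. A Week 12 call alone does not settle how a patient counted earlier is treated.
5. Align Sections 7.2 and 8.2.19 on withdrawal of consent: offer the final visit and omit it only if the patient refuses.

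The cost is a few sentences, one column in a listing, and one telephone call for each of the few early leavers.

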## 8.3. Additional Optional Procedures

During the treatment period optional procedures may be performed at visits following relapse or disease progression. Table 8-23 outlines these procedures.

Table 8-23 Optional Procedures and assessments following relapse or disease progression

Assessment or Procedure	Explanation	
Tumour tissue biopsy (new	Assessments to be performed:	
tumour tissue biopsy will be	• Optional: CD20 and CD37 expression in tumour by	
performed surgically)	immunohistochemistry	

Assessment or Procedure	Optional: Gene expression analysis in tumour (DNA, RNA, proteins) to evaluate the relationship between antitumour activity and NHL-related genes.	
	Note : If FFPE block not biobanked at CCLS, preparation of the 5μM FFPE slides for the respective analyses only after Sponsor request	

